**Aim 2:** Conduct a randomized controlled trial with 500 individuals with type 2 diabetes and medication nonadherence. The trial will compare the effect of usual care and the intervention on medication adherence and physiologic risk factors including A1c, blood pressure and low density lipoprotein cholesterol (primary outcomes), and quality of life and self-efficacy (secondary outcomes).

This innovative approach would be a major shift in how we help patients in under resourced areas living with chronic diseases commit to taking medications, improving health and eventually reducing health disparities.

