### Power Calculations and Sample Size

This study is powered to detect clinically meaningful differences in changes in medication adherence, A1c, blood pressure and LDL-cholesterol between either of the intervention arms compared with the usual care arm. The secondary outcomes are based on surveys (disease acceptance, quality of life). To consider the clustering of patients within town, we used a variance inflation factor  $D = [1 + \rho(m - 1)]$ , where  $m$  is the number of participants per community and  $\rho$  is the intra-class correlation (ICC). We conservatively estimate that we will have at least 80 clusters, corresponding to an average of 6-8 participants per cluster, with ICC=0.01 and 0.05 yielding  $D=1.084$  and  $1.419$ , respectively. Dividing the sample size per group  $N$  by  $D$  gives  $N_{\text{EFF}}$ , the effective sample size. In the Encourage study, those reporting nonadherence at baseline demonstrated ICCs in the range of 0.001-0.015 for most measures. To be conservative because we include new communities, we present power calculations for ICC=0.01-0.05. We observed 20% attrition over one year in the Encourage study and although attrition is likely to be lower over 6 months, we assume 20% attrition here, leaving 200 participants per group. Table 7 displays the detectable differences in adherence proportions and the difference in mean changes between groups detectable with 80% power using 2-sided  $X^2$  and t-tests with  $\alpha=0.05$ . We used variances based on the Encourage sample reporting nonadherence at baseline. We hypothesize that the intervention will result in improved medication adherence. Because eligibility requires low adherence at baseline, we expect low acceptance at baseline. Starting with low baseline values by design eliminates ceiling effects and allows us to reasonably anticipate large changes in the intervention groups and only modest changes in the control arm, as was seen in a storytelling intervention directed at blood pressure. For  $N=200$  per group, the difference in rates of medication adherence treated as a binary outcome detectable with 80% power depends on the proportion observed in the intervention group. If adherence is only 20% in the intervention group, then we can detect as different rates among the control group of 8.8-10.1%, depending on ICC. These rates are both lower than we anticipate for the intervention group and considerably higher than we expect in the control group. Assuming 200 participants per group we will have 80% power using 2-sided t-tests to detect differences of 0.28-0.32 standard deviations for continuous outcomes. Using variance estimates from Encourage data for change in the Diabetes Distress Score, another validated psychometric instrument, this translates into detecting differences as small as 3.7-4.4% of the range. Similarly, detectable differences for change in A1c are in a clinically meaningful range from 0.41-0.48%. We anticipate detectable differences for systolic blood pressure of 3-4 mmHg, and for LDL-cholesterol of 6.7-8.1 mg/dL.

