The primary analysis will test the hypothesis that medication adherence treated as a binary outcome will be greater in the treatment arm than the control arm at follow-up. As above, the primary unadjusted hypothesis test will use either a  $X^2$  test or logistic regression with GEE depending on the magnitude of observed ICCs. Statistical significance will be judged by  $p < 0.05$  for either the  $X^2$  test or the coefficient for study group in regression models. The intervention group will be compared to the control group; further analyses will use logistic regression with GEE to model adjusting for any covariates that were imbalanced between groups at baseline, and will then proceed to examine regression models adjusted for the covariates described in Table 6.

Analysis for A1c, blood pressure and LDL-cholesterol and the secondary outcomes will be very similar to the analysis of medication adherence described above. We note that we will also be able to analyze adherence as a continuous outcome as a secondary analysis using the following approach. For each of these continuous or ordinal measures, we will begin by calculating the change from baseline to 6-month follow-up for each participant. These change scores will be the units of analysis and we hypothesize greater change among the intervention groups compared to the control group. We will proceed to examine summary statistics, histograms, and scatter plots of the measured outcomes for outliers and data trends. We will then test for unadjusted differences in changes between the intervention and control groups using t-tests, Mann-Whitney-Wilcoxon tests, or regression models with GEE to account for clustering, as appropriate for the variable and ICC. Similar to above, we will then proceed with more sophisticated analyses in stages, first adjusting for baseline values of outcome variables, then for any factors that were imbalanced at baseline and finally adjusting for covariates mentioned above.

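### The plan allows for up to 20% attrition but gives no as-assigned analysis set or missing-outcome rule, so the default is a complete-case analysis that is biased if loss is related to adherence and differs by arm

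*Combined protocol and SAP*

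**What the plan says.** Study Aims sets the size: "Conduct a randomized controlled trial with 500 individuals with type 2 diabetes and medication nonadherence". Power Calculations and Sample Size takes its attrition figure from the earlier trial ("We observed 20% attrition over one year in the Encourage study and although attrition is likely to be lower over 6 months") and then writes "we assume 20% attrition here, leaving 200 participants per group". That is the only use made of attrition in the analysis plan.

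Data Analysis defines the primary test as a comparison of whether "medication adherence treated as a binary outcome will be greater in the treatment arm than the control arm at follow-up". The test is chi-square or logistic GEE, depending on the observed ICC. A1c, blood pressure, LDL-cholesterol, the secondary outcomes and continuous adherence are analysed as changes: "These change scores will be the units of analysis and we hypothesize greater change among the intervention groups compared to the control group". GEE, and the repeat with towns as random effects, are there to handle clustering.

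Participant Retention sets two triggers for arranging the follow-up interview and visit. Controls are contacted during month 6. Intervention participants are contacted once their last peer session has taken place.

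**The concern.** There is one follow-up. A participant without a 6-month value has neither a follow-up adherence status nor a change score, so none of the named methods can use that participant. Neither GEE nor the random-effects repeat changes this, and baseline adjustment still needs an observed outcome. The analysis section contains no intention-to-treat statement, analysis set, missing-data assumption, imputation rule, sensitivity analysis for loss or comparison of loss by arm.

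A complete-case comparison is safe when loss is unrelated to adherence, but that is hard to take for granted here. Intervention participants are asked for 13-16 calls, daily logging and homework, while controls receive a DVD and handout. Because intervention follow-up is arranged after the last coaching session, someone who stops taking calls has no clear point at which follow-up is triggered, while a disengaged control is still contacted at month 6. If non-adherent people are lost more readily from one arm, the completers no longer represent the groups formed by randomising towns. With no rule fixed in advance, the handling of missing outcomes could also be chosen after the results are known.

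**Working it through.** **Inputs from the documents.** 500 enrolled; 20% attrition; 200 per group analysed; two-sided tests at 0.05 ("Statistical significance will be judged by" p < 0.05); design rates of 20% adherence in intervention against 8.8-10.1% in control; stated design effects D = 1.084 and 1.419.

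**Assumptions, not in the documents.** Loss of 20/20, 25/15 or 30/10% (intervention/control); true adherence 20% in both arms (range 10-30%); adherence among those lost equal to, half of, or zero relative to the arm's rate.

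**The plan's own figure.** 500/2 × (1 − 0.20) = 200 per group. It reproduces, and it shows that power is calculated on completers.

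**Effect of loss when there is no true effect.** With true adherence p, loss l and adherence q among the lost, observed adherence is (p − l·q)/(1 − l). The chance of a significant result favouring the intervention is 1 − Φ[(1.96·SE₀ − δ)/SE₁]. Here δ is the expected observed difference, SE₀ the pooled standard error and SE₁ the unpooled one.

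Worked case, 25/15 loss with all lost non-adherent:
- Observed rates: 0.20/0.75 = 26.7% of 187.5 and 0.20/0.85 = 23.5% of 212.5, so δ = 0.0314.
- SE₀ = √[0.25 × 0.75 × (1/187.5 + 1/212.5)] = 0.0434; SE₁ = 0.0435.
- (1.96 × 0.0434 − 0.0314)/0.0435 = 1.23, giving 11%.

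The other cases, at p = 20% and D = 1:

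| Who is lost | 20/20 | 25/15 | 30/10 |
|---|---|---|---|
| Unrelated to adherence, both arms | 2.5% | 2.5% | 2.5% |
| All lost non-adherent, both arms | 2.5% | 11% | 31% |
| Intervention losses non-adherent, control losses random | 22% | 35% | 52% |
| Intervention losses at half the adherence rate, control losses random | 9% | 13% | 18% |

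Simulation of 250 per arm agrees with these. At D = 1.419 the 11%, 31%, 22% and 52% become about 9%, 23%, 17% and 39%. Over true adherence of 10-30%, the 11% ranges from 7% to 16%. With all 500 outcomes known, the rate is 2.5% throughout.

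**Sensitivity of a result like the one planned for.** Observed 40/200 against 20/200 gives p = 0.005. Suppose none of the 50 lost intervention participants is adherent:
- If 5 of the 50 lost controls are adherent (10%, the rate in observed controls), 40/250 against 25/250 gives p = 0.046, or 0.055 at D = 1.084.
- If 6 are adherent, 40/250 against 26/250 gives p = 0.064.

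**Would counting the missing as non-adherent settle it?** No. With no true effect and loss unrelated to adherence, but more controls lost (15/25), expected rates become 0.20 × 0.85 = 17% against 0.20 × 0.75 = 15%, and the favourable false-positive rate is about 9%. At 10/30 (18% against 14%) it is about 23%. If only intervention losses are non-adherent, it is still about 21% at 20/20.

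**The case against.** - **Exclusion is not stated.** A reader might infer that the plan excludes lost participants by rule. No sentence does so. What stands is narrower: the named methods need a 6-month value and no rule covers its absence, so complete-case is the default.
- **20% is not a forecast.** It was one-year loss in the earlier trial, and the plan expects less at 6 months. It is a cautious planning figure, and less loss means less bias.
- **Unequal loss alone is not enough.** A reader might infer that different loss rates by themselves could produce a positive result. They do not: the first row of the table stays at 2.5%. The loss must be related to adherence.
- **The direction is not known.** Intervention participants have far more contact through their coaches, although controls get one more staff call and three postcards. Both arms receive the gift card only at the second visit, and visits may be at home. Retention could be better in the intervention arm. If it lost 15% against 25% in control, all non-adherent, the favourable false-positive rate would fall to about 0.4% and a real benefit would be understated. The documents do not settle which way bias would run.
- **Some protection exists.** Retention contacts in both arms and a separate follow-up telephone interview are planned. They may reduce loss, but they do not bring a lost participant into the analysis.

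**Conclusion.** The point holds as a gap in the primary analysis: attrition is budgeted for in the sample size, but nothing says how those lost are analysed or how the effect of loss is judged. Under no true effect, the favourable false-positive rate goes from 2.5% to about 11% and 31% at 25/15 and 30/10 loss if all those lost are non-adherent. It reaches about 22% at equal 20% loss if only the intervention arm loses non-adherers, and 9-18% under the half-rate pattern. These figures rest on assumed loss splits, 20% true adherence and no clustering; the stated design effects lower them but do not remove them.

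The documents do not support the stronger conclusion that a positive result would be produced by attrition, or that the intervention arm will lose more people. They do contain a route to engagement-related loss in the differing follow-up triggers. The text available for this review includes the whole analysis section, and the contents list shows no later analysis section. A missing-data plan elsewhere is unlikely but cannot be ruled out.

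**What to change.** In Data Analysis:
1. Analyse all enrolled participants in the arm assigned to their town, whatever coaching they received.
2. Multiply impute missing 6-month outcomes from baseline values, baseline Morisky items, randomisation strata and covariates, using a method that respects town clustering. With about 400 completers over 80-100 towns there are only 4-5 per town, so separate town indicators would be unstable. Anyone lost between the baseline telephone interview and the in-person visit also lacks baseline A1c, blood pressure and LDL, and the imputation must allow for that.
3. Prespecify a tipping-point analysis for binary adherence that varies the assumed adherence of those lost separately by arm. Imputation from baseline data does not cover loss that depends on the unseen outcome. Missing counted as non-adherent in both arms should be one scenario, not the test of robustness.
4. Report loss and its reasons by arm.

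In Participant Retention, reconcile the two triggers so that both arms are contacted at calendar month 6. Offer the Morisky items in the telephone interview already planned to everyone, including those who stopped coaching or decline the visit.

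The cost is plan wording, some extra analysis and a few more calls. The estimate may be less favourable or less precise.

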
### Data Analysis

The main hypothesis to be tested is that participants in the intervention group will have higher medication adherence and significantly greater improvement in A1c, blood pressure, LDL-cholesterol, and measures of quality of life; and fewer barriers to adherence compared to control patients. While medication adherence can be considered as a continuous variable, we will follow the literature and treat adherence as a binary outcome by classifying participants as non-adherent if measured adherence is <80% and adherent otherwise. Therefore, unadjusted testing of the main hypothesis will use two-sided  $X^2$  tests and statistical modeling will use logistic

regression. The other primary outcomes (A1c, blood pressure, LDL-cholesterol) and the secondary study outcomes of physical and mental functioning, as measured by the SF-12, diabetes distress, and barriers to adherence are all continuous or ordinal measures. As such unadjusted hypothesis tests for these outcomes will use t-tests or the Wilcoxon-Mann-Whitney test, as appropriate, and statistical modeling will use linear regression. Analysis will begin by calculating ICCs for each outcome to assess the magnitude of clustering; if the ICCs are found to be significantly non-zero with  $p < 0.05$  or with a point estimate greater than 0.01, testing of main hypotheses will use unadjusted regression models (logistic or linear, as appropriate) with Generalized Estimating Equations (GEE) to account for clustering. All regression models for outcomes with non-negligible ICCs will use GEE to account for clustering due to randomization at the town level, and will be repeated using mixed models treating the towns as random effects with results examined for consistency.

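### For A1c, blood pressure, LDL and the continuous secondary outcomes, the already planned baseline-adjusted model should be named the decisive test in place of the unadjusted change-score comparison: a free gain in precision

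*Combined protocol and SAP*

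**What the plan says.** All of this is in the protocol's Data Analysis section.

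- A1c, blood pressure and LDL-cholesterol are called primary outcomes alongside adherence. The named primary analysis concerns adherence only: "The primary analysis will test the hypothesis that medication adherence treated as a binary outcome will be greater in the treatment arm".
- For the three physiologic outcomes and the secondary outcomes, "we will begin by calculating the change from baseline to 6-month follow-up for each participant". Those change scores are the units of analysis.
- The test follows: "We will then test for unadjusted differences in changes between the intervention and control groups using t-tests", or a rank test, or regression with GEE, depending on the variable and the ICC. The opening paragraph says the same: "unadjusted hypothesis tests for these outcomes will use t-tests or the Wilcoxon-Mann-Whitney test". Where the ICC is not negligible, GEE is added but the main-hypothesis model stays unadjusted.
- Only then: "we will then proceed with more sophisticated analyses in stages, first adjusting for baseline values of outcome variables", followed by factors imbalanced at baseline and then by further covariates.

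The section does not say which of these stages decides the result for A1c, blood pressure, LDL or the secondary outcomes. The sentence setting p < 0.05 is written around the adherence test and does not settle it.

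**The concern.** Taking the change score subtracts the baseline with a slope of exactly 1. Follow-up values usually regress towards the mean, so the best-fitting slope is below 1 and full subtraction over-corrects. There are two consequences.

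1. **Precision.** The change-score contrast has a larger variance than the arm coefficient from a model that estimates the baseline slope from the same data.
2. **Chance imbalance.** If one arm happens to start higher, part of that gap reappears as an apparent difference in change. Randomization is stratified by region and town size only, so nothing in the design balances baseline A1c, blood pressure or LDL.

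At stake are the width of the confidence intervals for three outcomes called primary, and which result would be believed if the unadjusted and adjusted stages disagreed.

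**Working it through.** **Inputs from the documents** (Power Calculations and Sample Size): 200 analysed per arm; two-sided alpha 0.05; 80% power; D = 1.084 (ICC 0.01) and 1.419 (ICC 0.05); detectable difference 0.28-0.32 SD; A1c 0.41-0.48.

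**Assumed, because the available text does not give them:** the baseline/6-month correlation rho, taken over 0.3 to 0.9, and equal SDs at the two visits, relaxed below.

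**Step 1. The plan's own figure.** Detectable difference = (1.960 + 0.842) x sqrt(2/N_eff), with N_eff = 200/D.

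- D = 1.084: N_eff = 184.5, giving 0.292 SD.
- D = 1.419: N_eff = 140.9, giving 0.334 SD.

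The stated 0.28-0.32 is not reproduced. It matches D = 1.00 (0.280) to D = 1.30 (0.319). That mismatch is a separate matter. It does not enter the variance ratio below, but it makes rescaled detectable differences illustrative only.

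**Step 2. Variance of the two estimators.** With SDs s0 (baseline) and s1 (6 months), per participant:

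- change: s0² + s1² - 2·rho·s0·s1
- baseline-adjusted: s1²(1 - rho²)
- difference: (s0 - rho·s1)², which is never negative.

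So in large samples the adjusted estimate is never less precise, whatever rho is. With s0 = s1 the ratio of adjusted to change variance is (1 - rho²)/(2(1 - rho)) = (1 + rho)/2, and the information lost is (1 - rho)/2.

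**Step 3. Size.** Detectable differences are multiplied by sqrt((1 + rho)/2). The last column is the adjusted power at an effect for which the change-score test has 80%: Phi(2.802 x sqrt(2/(1 + rho)) - 1.96).

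| rho (assumed) | Information lost | A1c 0.41-0.48 becomes | Adjusted power |
|---|---|---|---|
| 0.3 | 35% | 0.33-0.39 | 94% |
| 0.5 | 25% | 0.36-0.42 | 90% |
| 0.7 | 15% | 0.38-0.44 | 86% |
| 0.8 | 10% | 0.39-0.46 | 84% |
| 0.9 | 5% | 0.40-0.47 | 82% |

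If the follow-up SD is 10% below or above the baseline SD, the loss is 33% or 18% at rho 0.5, and 25% or 8% at rho 0.7.

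**Step 4. Does clustering change this?** A simulation with 80 towns, 5 analysed per town (400/80), ICC 0.01 and 0.05, and the same rho between and within towns gave losses of 33-34% (rho 0.3), 25-27% (0.5), about 16% (0.7) and 5% (0.9). Within simulation error these agree with the formula.

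**Step 5. Chance baseline gap.** The SE of the baseline difference is sqrt(2/N_eff): 0.104 SD at N_eff 184.5 and 0.119 SD at 140.9. A gap of 0.2 SD or more in either direction is 1.92 or 1.68 standard errors, with probability 5.5% or 9.3%. A gap g moves the expected change difference by -(1 - rho)g:

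- rho 0.5: 0.5 x 0.2 = 0.10 SD
- rho 0.7: 0.3 x 0.2 = 0.06 SD

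The SD of change is sqrt(2(1 - rho)) single-visit SDs, that is 1.00 and 0.775. In change-SD units the shifts are therefore 0.10 and 0.06/0.775 = 0.077, or 24% to 36% of the stated 0.28-0.32. In the Step 4 simulation the change-score estimate correlated with the baseline gap at about -0.5 (rho 0.5) and -0.4 (rho 0.7); the adjusted estimate did so at about 0.

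**Step 6. Is the better estimate already planned?** Regressing change on arm and baseline lowers the baseline slope by exactly 1 and leaves the residuals, and hence the arm coefficient, unchanged compared with regressing the 6-month value on arm and baseline. The plan's first adjusted stage therefore already yields the recommended estimate.

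**The case against.** **Baseline adjustment is already planned.** This is true, and it limits the point. A reader might infer that the baseline values go unused, but the first of the staged models adjusts for them. The gap is that this stage is not named as decisive.

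**The unadjusted test is valid.** This also stands. A reader might infer a biased test or an inflated type I error. Over repeated randomisations a chance baseline gap causes neither; it affects the one result that is realised.

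**The trial is powered for the test it plans.** Correct. The power section works with differences in mean change, so the stated power does not depend on adjustment. Reading the loss as a power shortfall would be wrong.

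**The size rests on assumptions.** No correlation is given, so a fixed loss such as 15-25% cannot be read from the documents. It corresponds to rho 0.5-0.7 with equal SDs. The direction does not depend on rho; the size does.

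**Imbalance is not likely.** At least 80 towns are expected, which is not few, and a 5.5% to 9.3% probability of a 0.2 SD gap is modest. The argument is that protection costs nothing, not that a gap should be expected.

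**Adjustment is not automatically better if baseline differences are systematic.** This is the strongest objection. Under Randomization, the first enrollee fixes a town's arm and later residents join a town already allocated. If that produced systematic baseline differences, the change-score and adjusted analyses could answer different questions. That calls for showing both results; it does not favour leaving the choice open.

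**Conclusion.** The point holds as a free improvement, not as an error of validity. For A1c, blood pressure, LDL and the continuous secondary outcomes, the first-line test is the less precise of two planned estimators, and the plan does not say which one counts. With equal SDs and an assumed rho, the loss is 25% of the information at rho 0.5, 15% at 0.7, and 35% to 5% across 0.3 to 0.9. A 0.2 SD baseline gap would move the change-score result by 0.06-0.10 SD at rho 0.7-0.5. The rescaled A1c figures are illustrations, because the stated detectable range does not follow from the stated design effects. The formulas concern comparisons of means and do not cover outcomes analysed by a rank test. Binary adherence, the named primary analysis, is outside the point.

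**What to change.** In Data Analysis, where the change-score test is described, prespecify before outcome data are seen:

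*For A1c, blood pressure, LDL-cholesterol and each continuous secondary outcome, the decisive test is the arm coefficient from a linear model of the 6-month value on arm and baseline value, accounting for clustering by town. The unadjusted comparison of change is supportive.*

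Using change as the outcome in that model gives the same coefficient, so either form will do. Report the adjusted and unadjusted results side by side, with baseline means by arm. A material disagreement would then prompt a look at whether recruitment after town allocation produced systematic baseline differences.

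The cost is a change of wording. The baseline values are already collected and the adjusted model is already planned; no participants, visits or procedures are added, and the adherence analysis stays as it is.
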